10.3. Vital Signs

Summary statistics (mean, standard deviation, median, min and max) of vital sign measurements and changes of measurements from predose for vital sign at each time point will be reported for pooled *hMaxi-K* and placebo in Table 14.3.4.3.

Individual vital sign records will be displayed in Listings 16.2.8.1 and 16.2.8.2.

10.4. ECGs

Using the ECG overreader results, frequency and percentage of subjects in different degrees of QTcF categories (QTcF > 450, > 480 and > 500 msec) will be tabulated by treatment at each scheduled timepoint in Table 14.3.4.4. Summary statistics of ECG test parameters, ventricular heart rate (bpm), PR interval (ms), QRS duration (ms), QT/QTc (ms), P-R-T axes, average RR (ms), QTcB (ms), QTcF (ms), and change of these parameters from pre-dose to each post-dose timepoint will be calculated Table 14.3.4.5.1 for pooled *hMaxi-K* and placebo and Table 14.3.4.5.2 for 16,000 ug and 24,000 ug *hMaxi-K* group.

ECG overread overall assessment records will be displayed in Listing 16.2.8.3.1 and individual ECG site reading parameters will be listed in 16.2.8.3.2.

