2.1 Objectives

The primary objective of this study is to evaluate occurrence of adverse events and their relationship to a single treatment of approximately 20 to 30 bladder wall intramuscular injections of *h*Maxi-K compared to placebo (PBS-20% sucrose). Two dose levels (16000 µg and 24000 µg) in females with moderate OAB/DO of \geq six months duration are initially planned. In each dose level, 6 participants will receive *h*Maxi-K and 3 will receive placebo. **Pending safety and efficacy results for the 2 doses that are planned, the protocol may be amended to investigate additional doses in this study.**

The secondary objectives of this study are to evaluate the following safety parameters:

- Clinical laboratory tests- changes from baseline
- Electrocardiogram change from baseline
- Physical Examination- changes from baseline

These changes will be evaluated primarily at the individual level, through clinical assessment of outliers supported by descriptive statistics.

Additional secondary efficacy objectives focus on the potential activity of intramuscular injections into the bladder wall of *h*Maxi-K compared to placebo. Two dose levels (16000 µg, and 24000µg) in female participants with moderate OAB/DO of \geq six months duration are initially planned. Individual efficacy parameters that will be evaluated as secondary endpoints are:

- Mean number of micturitions per 24 hours –change from baseline
- Mean volume per micturition – change from baseline
- Mean number of Urge Incontinence episodes –change from baseline
- Overall bladder capacity – change from baseline (as defined in section 6.1)

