14. In the judgment of the investigator any condition that would interfere with participation in the study (including geographical inaccessibility), that would contraindicate the administration of study medication or interfere with the study evaluations (e.g, potentially poor compliance in completion of diaries).
15. A current malignancy (basal cell carcinoma is not an exclusion).
16. Had within six months prior to enrollment any of the following:
- Myocardial infarction
 - Cerebrovascular accident
 - Uncontrolled hypertension (systolic >160 or diastolic >100 mmHg)
 - Arrhythmia
 - Congestive heart failure (dyspnea on minimal exertion or while supine)
 - Unstable angina (chest pain greater than three times weekly while on therapy)
 - Required treatment with calcium channel, beta-blocker medication, nitrates, or anti-epileptic drugs
17. Latex allergy (unless the facility can treat the participant with all latex free supplies).
18. Allergy to lidocaine, xylocaine or other local anesthetics.
19. Known current drug addiction and/or alcohol abuse.

20. Mental or legal incapacity.
21. Abnormal screening ECG as defined by the over reader (some abnormalities considered benign may be acceptable with the written consent of the Sponsor).

NOTE: Sinus bradycardia of 50-59 bpm is permissible. Other abnormalities that can be normal variants (and considered clinically insignificant) may be permissible. However, participants with such abnormalities cannot be randomized without review of their medical history and prior written approval of the Sponsor (or designee).

22. QTc of ≥ 450 ms (via 12-lead resting ECG using both Fridericia's and Bazett's formula) and/or family history of sudden death or participants with a family history of long-QT Syndrome.
23. Any current treatment or treatment within the last 14 days for OAB including herbal preparations. Botox within the last 6 months.
24. If the participant has used a bladder-training program, she must still fulfill inclusion criteria for symptoms, and exercise/training program must be continued without change.
25. History of urinary retention, or residual bladder volume > 200 ml) (evaluated by bladder scan).

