- A blinded code must be broken only in exceptional circumstances when knowledge of the study medication is essential for treating the participant.

Follow-up Procedures

- The Investigator should take all appropriate measures to ensure the safety of the participants, notably he/she should follow-up the outcome of any Adverse Events (clinical signs, laboratory values or other, etc.) until the return to normal or until stabilization of the participant condition.
- In the case of any Serious Adverse Event, the participant must be followed up until clinical recovery is complete and laboratory results have returned to normal, or until progression has been stabilized.
- In case of any Serious Adverse Event brought to attention of the Sponsor.

ECG Monitoring

In case of prolongation of $QT_cF \geq 500$ ms, or an increase in $QT_cF \geq 60$ ms from baseline, a blood sample should be drawn for potassium, calcium, magnesium and a plasma assay for *hSlo* cDNA with PCR. The *hSlo* analysis will be done by the under the direction of [name]. of the Department of Urology Research Laboratory, Albert Einstein College of Medicine.

A cardiologist should be consulted, and the participant should continue to have his or her ECG monitored until the ECG abnormality resolves or becomes stable and part of the patient's new medical history.

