
Objectives:
 
Primary: The primary objective of this study is to evaluate occurrence of Adverse Events and their relationship to hMaxi-K following multiple intramuscular (IM) injections into the bladder wall. Two dose levels (16,000 µg and 24,000 µg by IM injection into the bladder wall) in females with moderate OAB/DO of ≥ six months duration are initially planned.
 
 • Treatment Emergent Adverse Events (TEAEs) – frequency and percentage of TEAEs, TEAEs by maximum severity and by relationship to study drug by treatment; summary of any AEs resulting in discontinuation of administration of study drug, serious adverse events (SAEs), and deaths during the study • Secondary: The secondary objectives of this study are to evaluate the following safety parameters: 
 – Clinical laboratory tests - changes and shift (whether the tests are within clinical normal range, whether they are clinically significant) from baseline by treatment – Electrocardiogram – change and shift from baseline (per ECG over-reader) by treatment – Vital Signs (systolic and diastolic blood pressure, and pulse rate) - change and shift from baseline 
The last assessment made prior to dosing of double-blind study drug will be used as the baseline for all analyses of these safety parameters.
 
In addition, efficacy parameters will be evaluated as change from baseline compared to placebo. Comparisons will be made between combined placebo (N = 6) vs. 16,000 µg (N = 6) and 24,000 µg (N = 6) active hMaxi-K group separately, and also between combined placebo and combined active group (N = 12), as well as between treatment comparisons for a dose response analysis. Efficacy evaluations will include the number of micturitions per day, volume per micturition, urgency episodes (1 or greater on urgency scale), and incontinence episodes from voiding diary, and pad weight. Efficacy evaluations will also include the following cystometric evaluations performed by the overreader at week 4 and 24: 1) Detrusor overactivity ≥ 5 cm H₂O (yes/no- INCLUSION CRITERIA); 2) Volume at first desire to void; 3) Detrusor pressure at beginning of voiding (prior to onset of first contraction, either volitional or involuntary); 4) Volume at first involuntary contraction; if detrusor overactivity (DO) present-Not applicable if no DO present; 5) Maximum detrusor pressure at FIRST contraction.
	

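### SAP Table 14.3.4.4 has no category for the protocol's QTcF change trigger (a rise of 60 ms or more), so a participant who meets it can appear in no row

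*SAP*

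**What the plan says.** Protocol 9.6 (ECG Monitoring) sets a trigger with two limbs, one absolute and one for change: "In case of prolongation of $QT_cF \geq 500$ ms, or an increase in $QT_cF \geq 60$ ms from baseline, a blood sample should be drawn". The blood sample also covers an *hSlo* assay, and the protocol then calls for cardiology consultation and continued ECG monitoring.

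SAP 10.4 categorises overread QTcF in Table 14.3.4.4 by absolute value only: "frequency and percentage of subjects in different degrees of QTcF categories (QTcF > 450, > 480 and > 500 msec"). Change is handled separately as group summary statistics: "change of these parameters from pre-dose to each post-dose timepoint will be calculated Table 14.3.4.5.1 for pooled *hMaxi-K* and placebo", with Table 14.3.4.5.2 giving the two dose groups. For individual data, "ECG overread overall assessment records will be displayed in Listing 16.2.8.3.1 and individual ECG site reading parameters will be listed in 16.2.8.3.2".

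Two statements set expectations for these outputs. Protocol 2.1 says of the laboratory, ECG and physical examination changes: "These changes will be evaluated primarily at the individual level, through clinical assessment of outliers supported by descriptive statistics". The SAP synopsis promises for the ECG "change and shift from baseline (per ECG over-reader) by treatment". SAP 10.5 adds no other safety measure, and SAP 14 declares no departure from the protocol.

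**The concern.** The protocol defines what counts as a notable QTcF event in an individual, and one of its two limbs is a change from baseline. The only SAP table that counts individuals by QTcF ignores change. Entry requires a low QTc (exclusion 22 rules out "QTc of ≥ 450 ms (via 12-lead resting ECG using both Fridericia's and Bazett's formula")), so a participant can rise substantially and still finish below the table's lowest cut-point.

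ECG change is a declared secondary safety objective for a potassium-channel gene product. The protocol's account of the earlier erectile dysfunction trial records a borderline QTc prolongation, judged unrelated. With six active participants per dose, the useful output is a count of who crossed the protocol's own line, by arm. As planned, the report could show zeros in every QTcF row for an arm in which a participant had met the trigger.

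**Working it through.** The plan states no figure to reproduce. The check compares two sets of thresholds.

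**Inputs**
- Protocol trigger (9.6): QTcF ≥500 ms, or rise ≥60 ms from baseline.
- SAP rows (10.4): QTcF >450, >480, >500 ms.
- Entry limit (Protocol 4.3, exclusion 22): QTc ≥450 ms excluded, so screening QTcF is at most 449 ms in whole milliseconds.
- Six active participants per dose, 12 pooled (Protocol 2.1; SAP 3.2).
- Assumption: lowest baseline examined is 350 ms. The documents give no baseline distribution.

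**Change limb.** Let *b* be baseline and *q* the post-dose value. The trigger is met when *q* ≥ *b* + 60. No SAP row applies when *q* ≤ 450. Both can hold only if *b* + 60 ≤ 450, that is *b* ≤ 390.

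| Baseline | Baseline + 60 | SAP rows at that value |
|---|---|---|
| 370 | 430 | none |
| 380 | 440 | none |
| 390 | 450 | none |
| 391 | 451 | >450 |
| 400 | 460 | >450 |
| 420 | 480 | >450 |
| 440 | 500 | >450, >480 |
| 449 | 509 | >450, >480, >500 |

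Whole-millisecond pairs with baseline 350 to 449 ms and post-dose values up to 600 ms were enumerated. Of these, 861 meet the trigger and fall in no row, with baselines from 350 to 390 ms and post-dose values from 410 to 450 ms. The count agrees with 41 + 40 + … + 1 = 41 × 42 / 2 = 861. It describes the thresholds and is not a probability.

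**Absolute limb.** A value of exactly 500 ms meets the protocol's ≥500 but not the SAP's >500. It is still counted under >450 and >480. No value of 500 ms or more falls in no row.

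**What the group summaries would show.** Take one participant at 380 to 445 ms, a change of +65 ms, and assume the others in the group change by 0.
- Dose arm of 6: mean = 65/6 = 10.8 ms; SD = 65/√6 = 26.5 ms.
- Pooled active group of 12: mean = 65/12 = 5.4 ms; SD = 65/√12 = 18.8 ms.

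She is 1/6 = 17% of her arm, or 1/12 = 8% of the pooled group. SAP 10.2 and 10.3 specify minimum and maximum for laboratory tests and vital signs. SAP 10.4 does not, and SAP 13.2 guarantees only N, mean and SD. The largest individual change is therefore not assured in any ECG table.

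**The case against.** The case for leaving the table alone has several parts.

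- **The cut-points have a basis.** Protocol Appendix A grades prolonged QTc from 0.45 to 0.48 sec (Grade 1) and above 0.48 sec (Grade 2), and grades no change from baseline. The >450 and >480 rows follow that scale. This stands as an explanation of the rows. It also means that 380 to 445 ms reaches no Appendix A QTc grade, so the adverse event tables cannot be relied on to show it.
- **Protocol 9.6 is a monitoring instruction.** Nothing in the protocol requires trigger events to be tabulated. That is correct. A reader might infer that a participant could miss her blood sample or cardiology review; the documents do not support this, because the action is taken on the ECG and not on a table.
- **Individual data are listed.** With at most 18 planned participants and four scheduled post-dose ECGs each (Visit 2 at 2 hours, Visits 3, 5 and 8), a reader could find a 60 ms rise by subtraction in Listing 16.2.8.3.2, and an SD of 26.5 ms would prompt a look. This stands in part. That listing holds site readings, while the table uses overreads, which Protocol 6.5.2 makes the final interpretation. The overread listing is described as covering only the overall assessment.
- **The table shells may contain more.** They are a separate document and were not available, so this stays open.

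A reader might also infer that the >500 versus ≥500 mismatch lets a participant drop out of the table. It does not: a value of exactly 500 ms appears in two rows.

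**Conclusion.** The gap is real and confined to reporting. Table 14.3.4.4 cannot identify anyone who meets the protocol's change trigger. With a baseline QTcF of 390 ms or less, such a participant may appear in no row; with 391 ms or more she is counted but not identified as a rise of 60 ms or more. No other output described in the SAP counts these participants from the overread data. That falls short of the individual-level evaluation of outliers in Protocol 2.1 and of the change and shift per over-reader in the SAP synopsis, for which SAP 10.4 provides no shift analysis.

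The stake is one or more participants uncounted, each 17% of a dose arm. How likely this is cannot be judged, since the documents give neither a baseline QTcF distribution nor an expected rate of such rises. The 390 ms limit follows from the thresholds alone and does not depend on the assumed 350 ms floor. Baseline is taken as the last assessment before dosing, as the SAP synopsis defines it. The ≥500 difference is a boundary detail affecting one value.

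**What to change.** In SAP 10.4, Table 14.3.4.4:

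1. Add a row for QTcF increase ≥60 ms from the last pre-dose value, by treatment and timepoint, using the overread data.
2. Add a row for the same increase at any post-dose ECG, including unscheduled ones. The table now covers scheduled timepoints only, so the first row alone would not count every participant who meets the trigger. State which reading is used if an unscheduled ECG has no overread.
3. As a minor alignment with Protocol 9.6, change >500 to ≥500.

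The cost is two rows and one symbol, computed from ECG data the study already plans to collect. No clinical rule, visit or sample size changes. With rows 1 and 3 in place, every scheduled overread value that meets either limb of the trigger falls in a matching category.

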6.5.2 ECG

A 12-lead ECG will be performed at Screening (V1) Baseline (V2 -prior to treatment and 2 hours post treatment), V3, V5 and V8. These ECGs obtained at the study centers, will be forwarded to a central reader for final interpretation by a board-certified cardiologist or physician board certified in ECG interpretation. The over reader will return the results to the study center within 48 hours. This does not negate the responsibility of the staff conducting the study to initially review the ECG and to take appropriate clinical actions. The following parameters will be assessed: heart rate, rhythm, PR interval, RR interval, QT interval, QTcF, QTcB, QRS duration, and overall evaluation. For the Visit 2 pre-dose ECG, if abnormalities or clinically significant changes are noted from V1 screening ECG, then the investigator in conversation with the Sponsor and/or designee will determine the participant's eligibility to proceed with dosing.

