13.2. Statistical Conventions

For tables, sample sizes for each treatment group will be presented as totals in the column header ($N = xxx$), where appropriate. Sample sizes shown with summary statistics are the number (n) of participants with non-missing values.

Summaries for categorical variables will include only categories that subjects had a response in. Percentages corresponding to null categories (cells) will be suppressed. All summaries for continuous variables will include: N , mean, and SD . Other summaries (eg, median, quartiles, 5%, 95% intervals, CV or $\%CV$) will be used as appropriate. All percentages should be rounded and reported to a single decimal place ($xx.x\%$). If percentages are reported as integers, percentages greater than 0% but < 1% will be reported as < 1%, whereas percentages greater than 99% but < 100% will be reported as > 99%. A percentage of 100% will be reported as 100%. No value of 0% should be reported. Any computation of percent that results in 0% is to be reported as a blank. Summaries that include P values will report the P value to three decimal places with a leading zero (0.001). P values < 0.001 will be reported as < 0.001.

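### SAP 10.4 counts over-read QTcF categories at scheduled ECGs only and commits to listing individual intervals from the site read only, so the table cannot give the number of participants ever above a threshold or be traced to a listed over-read value

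*SAP*

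**What the plan says.** **Source and timing of the QTcF table.** SAP 10.4 opens with "Using the ECG overreader results, frequency and percentage of subjects in different degrees of QTcF categories", the cut-points being above 450, 480 and 500 ms. These "will be tabulated by treatment at each scheduled timepoint in Table 14.3.4.4". No any-time or highest-value row is named, and unscheduled ECGs are not mentioned.

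**Continuous ECG summaries.** The same section plans group statistics for heart rate, the intervals and both QTc corrections, with change from pre-dose at each post-dose timepoint (Tables 14.3.4.5.1 and 14.3.4.5.2).

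**Individual data.** Two ECG listings are named: "ECG overread overall assessment records will be displayed in Listing 16.2.8.3.1 and individual ECG site reading parameters will be listed in 16.2.8.3.2".

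**Status of the over-read.** Protocol 6.5.2 says the study ECGs "will be forwarded to a central reader for final interpretation by a board-certified cardiologist" or a physician board-certified in ECG interpretation. The SAP synopsis says ECG change and shift are to be reported from the over-reader.

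**Level of evaluation.** Of the laboratory, ECG and physical examination changes, Protocol 2.1 says: "These changes will be evaluated primarily at the individual level, through clinical assessment of outliers supported by descriptive statistics".

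**Extra ECGs.** Under Protocol 9.6, after a QTcF of at least 500 ms or a rise of at least 60 ms from baseline, "the participant should continue to have his or her ECG monitored until the ECG abnormality resolves" or becomes stable.

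**The concern.** The Protocol puts individual outliers first and descriptive statistics second, and it gives the central read the final word. SAP 10.4 puts the final read in the aggregate table, while the individual interval values it promises are the non-final site readings. A reader who sees one participant above 480 ms in the table has no promised over-read value with which to identify her or confirm the figure. Where the two reads differ, the listing and the table will disagree with no means of reconciling them.

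The table also answers a different question from the one a safety reader asks. It gives the number above a threshold at each visit. The usual question is how many participants were ever above it after dosing.

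The ECG matters in this trial. Protocol 5.2.1 names increased potassium efflux, with altered smooth muscle function in several organ systems, as a possible toxicity. Earlier hMaxi-K trials recorded a possibly related Mobitz type II block and a borderline QTc prolongation judged unrelated. Protocol 4.3 excludes a QTc of 450 ms or more, so a post-dose value above 450 ms would generally be new.

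**Working it through.** The plan states no figure on this point, so there is none to reproduce. The check is a comparison of sections and a count.

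**1. Does the over-read listing contain the intervals?** Protocol 6.5.2 names heart rate, rhythm, PR, RR, QT, QTcF, QTcB and QRS, and then overall evaluation as a further item. A listing described as overall assessment records therefore does not, by its wording, include QTcF. Other SAP sections are explicit:

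| Data | Individual listing promised |
|---|---|
| Cystometry (SAP 9.1) | Over-read parameters and site parameters |
| Laboratory (SAP 10.2) | Individual results, including repeats |
| ECG (SAP 10.4) | Over-read overall assessment; site parameters |

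**2. Do the continuous tables fill the gap?** They are group summaries: "change of these parameters from pre-dose to each post-dose timepoint will be calculated Table 14.3.4.5.1". Minimum and maximum are named for laboratory tests (10.2) and vital signs (10.3) but not for ECG. The general rule, "All summaries for continuous variables will include", guarantees N, mean and SD, with other statistics as appropriate. The highest QTcF in a group is therefore not assured even at a scheduled visit.

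**3. What can visit-by-visit counts say about participants ever affected?** Inputs: four scheduled post-dose ECGs (2 hours after dosing, then Visits 3, 5 and 8; Protocol 6.5.2), 6 participants per active dose, and 12 pooled active (SAP 3.2). If the count above a threshold at visit k is c_k in a group of N, the number ever above it at a scheduled post-dose ECG satisfies

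max(c_k) ≤ ever ≤ min(N, Σ c_k).

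For illustration, let c_k = 1 at all four ECGs:

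- Lower bound: 1 (the same participant each time).
- Upper bound: 1 + 1 + 1 + 1 = 4 (a different participant each time).
- Pooled active: each visit shows 1/12 = 8.3%; the ever-affected share is 1/12 = 8.3% to 4/12 = 33.3%.
- One dose group: each visit shows 1/6 = 16.7%; the ever-affected share is 1/6 = 16.7% to 4/6 = 66.7%.

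The pattern is assumed. It shows what the table cannot distinguish and is not a forecast.

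**4. What does the scheduled-only rule leave out?** ECGs taken under the Protocol 9.6 monitoring provision fall outside the scheduled timepoints and so outside Table 14.3.4.4. The 60 ms criterion in 9.6 also has no category in the table: a participant whose baseline is 390 ms or lower (450 − 60 = 390) can rise by 60 ms without exceeding 450 ms. Section 10.4 names no shift table, although the SAP synopsis promises shift from baseline.

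**The case against.** The strongest opposing case is that little is lost. Each part of it is taken in turn.

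- **The event leaves traces.** A scheduled over-read QTcF above 450 ms is counted in Table 14.3.4.4. The over-reader's overall assessment and the site intervals are listed per participant. Appendix A grades QTc prolongation from 0.45 s, and a prolongation recorded as an adverse event enters Listing 16.2.7.1. This stands. A reader might infer that a participant's worst over-read QTcF could vanish from every output; the documents do not support that.
- **Unscheduled over-reads may not exist.** Protocol 6.5.2 sends the scheduled tracings to the central reader, and neither document says whether follow-up ECGs are over-read. This stands. It would be wrong to say that unscheduled over-read values are being discarded. What can be said is that follow-up ECGs, however read, are outside the table.
- **The listing layout is in companion shells.** SAP 13 and 16 place it there, and the shells are not among the documents reviewed. They might add over-read columns. The criticism is therefore that the SAP text does not commit to them.
- **Safety review does not depend on these listings.** The over-read returns to the site within 48 hours (Protocol 6.5.2), and the DSMB reviews unblinded safety data (Protocol 5.2.2). This stands as to participant protection. It does not make the study report traceable.
- **With at most 18 participants, the site listing usually shows whether the same woman recurs.** This is largely right. The ambiguity remains where the site and over-read values fall on different sides of a threshold, and the documents give no discordance rate.
- **The long interval without a scheduled ECG between Days 29 and 169.** A reader might count this as part of the size of the problem. It belongs to the visit schedule, and neither change proposed here alters it.

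**Conclusion.** The point holds as a minor reporting gap with two parts. First, Table 14.3.4.4, being visit by visit and limited to scheduled ECGs, cannot give the number of participants ever above 450, 480 or 500 ms and excludes the Protocol 9.6 follow-up ECGs. In the illustrative pattern the same table is compatible with a fourfold range. Second, its counts cannot be traced to an over-read value that the SAP undertakes to list, which sits badly with the over-read's final status and the Protocol's individual-level approach.

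This rests on reading overall assessment as not including the intervals, as the separate items in Protocol 6.5.2 indicate, and on the companion shells not adding what the SAP text leaves out. How often the gap would matter depends on disagreement between site and over-read values and on the number of unscheduled ECGs; the documents give neither.

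**What to change.** Amend SAP 10.4 and the matching shells:

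1. Add to Table 14.3.4.4 a row for any post-dose ECG. It classifies each participant once by her highest post-dose QTcF, unscheduled ECGs included, using the over-read where one exists and otherwise the site value, flagged.
2. In Listing 16.2.8.3.1, show over-read heart rate, PR, QRS, QT, QTcB and QTcF, with change from pre-dose, for every over-read ECG, alongside the site values.

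The cost is one table row and extra listing columns. The scheduled ECGs give 6 × 18 = 108 listing rows for a full trial, from data already collected. The drawback is that the new row may mix over-read and flagged site values, so its footnote should say how many are of each kind. No visit, procedure or clinical rule changes.
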